5.2.1 Preparation of BEGEDINA

BEGEDINA should be visually inspected for particulate matter prior to administration.

The solution should be allowed to warm to room temperature (25°C) for 10-15 minutes prior to administration. The transfer procedures require strict adherence to aseptic techniques.

The required amount of BEGEDINA (calculated according to posology) should be drawn from the vial(s) using a sterile syringe and transferred into a 100 mL 0.9% saline solution infusion bag.

The infusion bag containing the diluted solution should be gently agitated to ensure thorough mixing of the product and diluent. Any unused BEGEDINA left in the vial should be discarded, as the product contains no preservatives. Any unused medicinal product or waste material should be disposed of in accordance with local requirements.

Detailed instructions regarding investigational agent preparation, handling and administration procedures are included in the Directions for Use and the Study Procedures Manual.

5.3 Management of Clinical Supplies

5.3.1 Packaging and Labelling

BEGEDINA will be packaged and supplied according to local legal requirements.

A label (in the local language) will be attached to the outside of each cases as well as to the immediate container (vial). The text will be compliant with local regulatory requirements and may include some of the following information:

- Protocol number
- Subject number/study center number
- Name, formulation, administration route and contents
- Lot number
- Investigator name or code
- Storage instructions

- Caution statement (for clinical study use only)
- Expiry date
- Sponsor name and address.

Each case includes Directions for Use with detailed instructions regarding investigational agent preparation, handling and administration procedures.

All study treatment supplies must be stored in accordance with the manufacturing instructions and according to local regulations.

5.3.2 Study Treatment Accountability

The investigator, a member of the investigational staff or a hospital pharmacist must maintain accurate records of receipt of all test articles, including dates of receipt. In addition, accurate records will be kept regarding when and how much study treatment is dispensed and used by each subject in the study. Reasons for departure from the expected dispensing regimen must also be recorded. This information must be recorded using the Drug Accountability Form, which must be available for inspection at any time.

All study medication supplies should be accounted for at the termination of the study and a written explanation provided for discrepancies. All unused study medication supplies and packaging materials are to be inventoried and returned to the CRO by the investigator. The investigator is not permitted to return or destroy unused clinical drug supplies or packaging materials unless authorized by the CRO.

5.4 Method of Assigning Subjects to Treatment Group

Once the subject meets all of the inclusion criteria and none of the exclusion criteria and has provided an informed consent, the study center will request the study medication assignment using the Interactive Voice Activated Response System (IVRS).

The subject will be randomized to either the active treatment group (BEGEDINA) or the conventional treatment arm (randomization ratio 1:1). Randomization will be stratified by the baseline GvHD severity grade to either Grade B GvHD or Grade C/D GvHD.

The randomization will be managed centrally.

Subjects must start study treatment the day of randomization. Specific randomization instructions will be provided in the study procedures manual.

5.5 Selection and Timing of Dose for Each Subject

All subjects randomized to the BEGEDINA treatment arm will receive 2.7 mg/m²/day IV for 5 consecutive days (Study Days 1, 2, 3, 4, 5) and on Study Days 10, 14, 17, 21, 24 and 28.

All subjects randomized to the conventional treatment arm will receive the treatment according to the relevant prescribing instructions (and/or standard practice of the center).

The rationale for the BEGEDINA dosing regimen and the choice of conventional treatment are discussed in Sections 4.3.1 and 4.3.2, respectively.

5.6 Blinding

Because the administration schedule could vary between the different conventional treatments chosen and also between the conventional treatments and BEGEDINA, the study will be conducted as an open-label study. The study team of the Sponsor and CRO (except the on-site monitors, pharmacovigilance and personnel as specified in the study-specific blinding plan), however, will be blinded regarding the study treatment up to database lock and general unblinding. The same holds for the independent hematologist who will adjudicate response.

The DSMB (see Section 6.2.6) members will receive unblinded outputs generated by a dedicated unblinded statistician and statistical programmer (both separated from the blinded study team members).

5.7 Prior and Concomitant Treatments

Prior medication refers to medication started within 30 days prior to screening and stopped prior to the first administration of the study treatment. Concomitant medication refers to medication started prior to and continued after the first administration of study treatment or taken any time after the first administration of the study treatment up to the follow-up visit.

Use of all concomitant medications will be recorded in the subject's eCRF, regardless of whether they are permitted or prohibited medications, up to Study Day 58 or up to 30 days after the last dose of study treatment, whichever is later.

The minimum requirement is that the drug name, dose, indication and the dates of administration are to be recorded. This will include all prescription drugs, herbal products, vitamins, minerals and over the counter medications. Any changes in concomitant medications will also be recorded in the subject's eCRF.

Any concomitant medication deemed necessary for the welfare of the subject during the study may be given at the discretion of the investigator. However, it is the responsibility of the investigator to ensure that details regarding the medication are recorded in full in the eCRF.

5.7.1 Excluded Medications

The following medications are prohibited during study (their use is a protocol violation and should be documented as such) and concomitant use during screening will result in subject exclusion:

- Agents for treatment of steroid-resistant acute GvHD other than BEGEDINA in the BEGEDINA arm or more than 1 single agent for treatment of steroid-resistant acute GvHD in the conventional treatment arm. Administration of any additional agent(s) for treatment of steroid-resistant acute GvHD within 28 days of randomization, either concomitantly or in succession, will be considered third-line therapy for treatment failure (i.e. salvage treatment; see [Section 5.8](#)).
- Any other investigational agents (not approved by the FDA or EMA for any indication) concurrently during study participation.

5.7.2 Allowed Medications and Therapies

- Blood products, including irradiated granulocytes.
- Steroid therapy and calcineurin inhibitors (or other ongoing GvHD prophylaxis, see [Section 5.7.2.2](#)) is allowed as concomitant baseline therapy per protocol ([5.7.2.4.1](#)). Subjects may continue any prior therapy used for prophylaxis at a stable dose from baseline as long as it has not been discontinued and restarted after initiating steroid treatment for acute GvHD (see [Section 5.7.2.2](#)).
- Subjects with stable disease (SD) or progressive disease ([Section 6.1.1.1](#)) at Study Day 28 or subjects who cannot tolerate the randomized study treatment may receive a third-line treatment for steroid-resistant acute GvHD at the investigator's discretion ([Section 5.8](#)).
- Other routine supportive care as per standard practice.

5.7.2.1 Conditioning Regimen for Hematopoietic Stem Cell Transplantation

There are no restrictions on the conditioning regimen administered before HSCT; it will be per local practice, the original disease, and the subject's clinical status and age. However, data on the conditioning regimen will be collected and might be used in exploratory analyses.

5.7.2.2 Prophylaxis for GvHD

There are no restrictions on GvHD prophylaxis (each study center will use appropriate prophylactic treatments according to local standards); subjects may continue any prior therapy used for prophylaxis at a stable dose from baseline as long as it has not been discontinued and restarted after initiating steroid treatment for acute GvHD. Patients who have developed steroid-resistant acute GvHD while on multiple ongoing GvHD prophylaxis may be enrolled, however, life expectancy must be carefully evaluated prior to their enrolment to fulfill with Exclusion Criteria no. 7.

After study start, baseline therapy with calcineurin inhibitors and steroids are to be administered as per [Section 5.7.2.4.1](#).

5.7.2.3 Premedication for Subjects Receiving BEGEDINA

Although allergic reactions have not been observed in Phase I-II studies, premedication, consisting of prednisolone 40 mg and diphenhydramine (e.g., 25-50 mg) (or another steroid equivalent and/or antihistamine drug), are recommended to be administered parenterally at least 30 minutes prior to the BEGEDINA infusion.

Note: for those subjects already on high doses of steroids, premedication with additional steroid may not be necessary (may be omitted at the discretion of the investigator).

5.7.2.4 Standard of Care for Subjects with Acute GvHD

All enrolled subjects will receive institutionally defined standard of care as described in Section 5.7.2.4.1. In addition, investigators should provide standard of care for prevention and treatment of viral infections, particularly if there is evidence of viral reactivation as discussed in Section 5.7.2.4.2 (unless qualifies as excluded medications, [see section 5.7.1](#)).

5.7.2.4.1 Concomitant Treatment

Alongside the study treatments, the following drugs will be administered to subjects in both treatment arms as baseline therapy

- Methylprednisolone IV at the dose of 2 mg/kg/day (or other steroid and dose equivalent)

- A calcineurin inhibitor (or other alternate, continuing GvHD prophylaxis) ([see also Section 6.2.4.2](#)), adjusted to therapeutic drug levels per study center standard practice.

They will be administered per the Principal Investigator's discretion and according to standard practice and institutional/international guidelines. Methylprednisolone or steroid equivalent dose may be escalated for worsening of acute GvHD as per Section 5.10. Tapering of steroids can start only after response (at least 1 stage in 1 organ) is observed and after at least 5 days of BEGEDINA or conventional treatment. A steroid taper rate of at least 10% of the dose per week, but not exceeding 25% of the dose per week, is recommended as summarized in Table 25 (see Appendix 1 in Section 12.1), with the goal of discontinuation of steroids by 10 weeks after initiating taper. Tapering may be commenced earlier or rate increased for documented strong safety indications (e.g., uncontrolled infection).

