4.0 INVESTIGATIONAL PLAN

4.1 Summary of Study Design

This will be a prospective, multicenter, randomized, open-label, phase II/III clinical study in which subjects will be randomly assigned in a 1:1 ratio to receive BEGEDINA treatment or the best conventional treatment. Randomization will be stratified by the baseline GvHD severity grade to either Grade B GvHD or Grade C/D GvHD.

The study will be conducted at approximately 30 bone marrow transplantation units in Europe, US and Canada. It is planned to enroll 184 subjects with steroid-resistant acute GvHD. The subjects will be randomized (1:1) to one of two treatment arms:

- BEGEDINA IV at a dose of 2.7 mg/m²/day for 5 consecutive days from Study Day 1 through to Study Day 5, and on Study Days 10, 14, 17, 21, 24, and 28.*
- Conventional second-line treatment: a single treatment (agent), chosen at the discretion of the investigator (physician's best choice) and based on the clinical conditions of the individual subject. The treatment will be given as per prescribing instructions (and/or standard practice of the center).

Patients in both arms are to continue (or initiate) baseline therapy of methylprednisolone (or other steroid equivalent) and calcineurin inhibitor (see Section 5.7.2.4.1).

*Please note: the term "Study Day" as used throughout the protocol is used in relation to the day that randomized study treatment started and not in relation to the day of transplant.

All subjects will undergo a screening visit to assess for eligibility and for screening assessments; this visit must take place within 2 days of Baseline. After screening, subjects will undergo randomization and the baseline visit, which is also the first day of study treatment (Study Day 1) (i.e., subjects must commence study treatment within two days of meeting eligibility). Study visits will be conducted at various timepoints (Table 19) through Study Day 180.

The experimental phase of the study will end for each subject on Study Day 180. An extended, long-term, observational follow-up is also planned in order to capture survival, response/relapse, glucose metabolism, health outcomes and safety data out to Study Day 180. Thus, the expected duration for an individual subject who completes the study according to the protocol will be approximately 6 months, including screening and 180-day follow-up.

Table 19 Schedule of Events

Study Day Visit Windows Assessments	Screening ^a	Experimental Phase																		Early Withdrawal	

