4.4 Selection of Study Population

4.4.1 Inclusion Criteria

Male or female subjects may be entered in the study only if they meet all of the following criteria:

1. Age ≥ 18 and ≤ 65 years of age.
2. Recipient of an allogeneic HSCT.

Note: Subjects with steroid-resistant GvHD following donor lymphocyte infusion post-HSCT are also eligible

3. Steroid-resistant acute GvHD, Grade II-IV, defined as:

- progressive disease (deterioration of at least 1 stage in 1 organ) after 3 days of primary treatment with methylprednisolone 2 mg/kg, or equivalent.

or

- lack of at least a PR after 7 days of primary treatment with methylprednisolone 2 mg/kg or equivalent.

or

- lack of a CR after 14 days of primary treatment with methylprednisolone 2 mg/kg or equivalent.

Note: Subjects who may have received an increase in their steroid dose treatment prior to randomization will be eligible for enrollment. An increase in steroid dose will not be considered as second-line therapy.

4. Evidence of previous myeloid engraftment (absolute neutrophil count $\geq 0.5 \times 10^9/L$).
5. Karnofsky Performance Status score $\geq 50\%$.
6. Adequate renal function as defined by serum creatinine $\leq 2 \times$ upper limit of normal (ULN) or calculated creatinine clearance (CrCl) of ≥ 30 mL/min using the Cockcroft-Gault equation: Calculated CrCl = $([140 - \text{age in years}] \times [\text{ideal body mass \{IBM\} in kg}]) / 72 \times (\text{serum creatinine value in mg/dL})$, where IBM = IBM (kg) = $([\text{height in cm} - 154] \times 0.9) + (50 \text{ if male, } 45.5 \text{ if female})$.
7. Subject must be willing and able to comply with study requirements, remain at the clinic, and return to the clinic for the follow-up evaluation, as specified in this protocol during the study period.
8. Able and willing to provide signed informed consent.

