6.2.4.2 Concomitant Medication and Supportive Therapy

Information on all concomitant medications will be collected for this study, including information on all concomitant therapy to treat acute GvHD. All pharmacologic and nonpharmacologic treatment used by study subjects to treat acute GvHD prior to screening should be recorded in the corresponding eCRF. This will include the treatment for HSCT procedure.

Subjects will continue to be treated with a stable dose of systemic steroid therapy until able to be tapered following response (at least 1 stage in 1 organ) to treatment (see section [5.7.2.4.1](#)). Subjects may also continue any prior therapy used for prophylaxis at a stable dose from baseline if the therapy agent was not discontinued and restarted after initiating first-line steroid treatment for acute GvHD. No other GvHD medications are to be introduced to subjects during the initial 28 days post-BEGEDINA administration unless disease has progressed. Addition of other agents prior to Study Day 28 would constitute failure to respond (endpoint OR at Study Day 28), however the subject will remain on study for follow-up.

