8.3.5.2 Analysis of Other Secondary Efficacy Endpoints

All other secondary and supportive analyses will be tested at a one-sided $\alpha=0.025$ significance level (where applicable), with no adjustments for multiplicity. These endpoints and their statistical analysis method are:

- Change from baseline in stages of GvHD by target organ at Study Day 28: shift tables displaying the frequencies for each possible change from baseline to Study Day 28.
- Cumulative incidence of chronic GvHD up to Study Day 180 will be graphically displayed by non-parametric cumulative incidence curve estimates. The null hypothesis of same cumulative incidences (up to Study Day 180) for both study treatments will be tested by a one-sided test stratified for the baseline GvHD severity grade, taken into account the competing risk of death. Stratified regression analysis of cause-specific hazards will be performed as supportive analysis in order to quantify the treatment effect in terms of hazard ratios and two-sided 95% CI. The cumulative steroid dose on Study Days 28, 56 and 90: descriptive statistics and non-parametric Wilcoxon-Mann-Whitney test stratified by for the baseline GvHD severity grade.
- Cumulative incidence of relapse up to Study Day 180 will be graphically displayed by non-parametric cumulative incidence curve estimates. The null hypothesis of same cumulative incidences (up to Study Day 180) for both study treatments will be tested by a one-sided test stratified for the baseline GvHD severity grade, taken into account the competing risk of death prior to diagnosis of relapse. Stratified regression analysis of cause-specific hazards will be performed as supportive analysis in order to quantify the treatment effect in terms of hazard ratios and two-sided 95% CI.
- Cumulative incidence of relapse-related mortality up to Study Day 180 will be graphically displayed by non-parametric cumulative incidence curve estimates. The null hypothesis of

same cumulative incidences (up to Study Day 180) for both study treatments will be tested by a one-sided test stratified for the baseline GvHD severity grade, taken into account the competing risk of transplant-related death (defined in Section 6.1.1.2). Stratified regression analysis of cause-specific hazards will be performed as supportive analysis in order to quantify the treatment effect in terms of hazard ratios and two-sided 95% CI.

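### The background steroid dose for subjects escalated before randomization is unclear, and the cumulative steroid test as described does not use the dose at entry

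*Combined protocol and SAP*

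**What the plan says.** Four places in the protocol bear on the background steroid dose.

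- Section 5.7.2.4.1 lists, for both arms, "Methylprednisolone IV at the dose of 2 mg/kg/day (or other steroid and dose equivalent". It then adds: "They will be administered per the Principal Investigator's discretion and according to standard practice and institutional/international guidelines". On reduction it says: "Tapering of steroids can start only after response (at least 1 stage in 1 organ) is observed", and also asks for at least 5 days of study treatment first, with an exception for strong safety reasons.
- Section 6.2.4.2: "Subjects will continue to be treated with a stable dose of systemic steroid therapy until able to be tapered following response". It gives no mg/kg figure and refers back to 5.7.2.4.1.
- Section 4.1: "Patients in both arms are to continue (or initiate) baseline therapy of methylprednisolone (or other steroid equivalent", again with no dose.
- Section 4.4.1, note to criterion 3: "Subjects who may have received an increase in their steroid dose treatment prior to randomization will be eligible for enrollment". No upper limit on the raised dose is stated.

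Cumulative steroid dose at Study Days 28, 56 and 90 is an other secondary endpoint. Section 8.3.5.2 analyses it by "descriptive statistics and non-parametric Wilcoxon-Mann-Whitney test stratified by for the baseline GvHD severity grade", at one-sided 0.025 without multiplicity adjustment. It names no term for the steroid dose at entry.

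**The concern.** Steroid is the main co-treatment in both arms of an open-label trial, and the total given is itself a tested endpoint. The protocol expects subjects who arrive on a raised dose: criterion 3 has a note for them, and section 5.7.2.3 mentions subjects already on high doses. Yet it does not state their starting background dose. About 30 sites could reasonably settle this in two ways.

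Whichever way it is settled, part of the spread in cumulative dose comes from a quantity fixed before randomization. If the analysis ignores that quantity, a real difference between the arms is harder to detect.

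**Working it through.** **1. The sections side by side, for a subject escalated before randomization**

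| Option from Study Day 1 | Fits | Sits badly with |
|---|---|---|
| Go to 2 mg/kg/day | the dose listed in 5.7.2.4.1; the first row of Table 25 | continuing a stable dose (6.2.4.2), if that means the current dose; the rule that taper follows response |
| Keep the raised dose | continuing (4.1, 6.2.4.2); investigator discretion (5.7.2.4.1) | the listed 2 mg/kg/day |

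The escalation guidance in section 5.10 does not settle it, because it concerns worsening or persistence despite second-line treatment, which has not begun at entry. Table 25 starts only at 2 mg/kg/day. Whether the taper rule governs the setting of the dose on Day 1, or only later reductions, is not said.

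**2. How far the two readings can differ**

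Total over 28 days without taper = 28 x daily dose. Entry doses above 2 mg/kg/day are assumptions.

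- 28 x 2 = 56 mg/kg
- 28 x 3 = 84 mg/kg (84/56 = 1.5-fold)
- 28 x 4 = 112 mg/kg (2-fold)
- 28 x 5 = 140 mg/kg (2.5-fold)

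The absolute totals are upper figures, since taper may begin earlier in responders.

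**3. Effect on the test**

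The plan gives no power, SD or effect size for this endpoint, so there is no figure to reproduce. A simulation shows the direction and rough size.

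- From the protocol: 184 subjects, 1:1 allocation, two grade strata, about 30 sites, stratified Wilcoxon test at one-sided 0.025.
- Assumed: log-SD 0.5; true log-ratio 0 or -0.2 (exp(-0.2) = 0.82, a reduction of about 18%); 10-50% escalated, to 3 or 5 mg/kg/day; either half the sites keep the raised dose and half use 2 mg/kg/day, or all sites keep it.
- 3000 runs per setting. Monte Carlo standard error near 75% power is sqrt(0.75 x 0.25 / 3000) = 0.8 points.

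*No true effect:* rejection is about 2-3% in every setting, with or without adjustment. Type I error is not inflated.

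*Log-ratio -0.2:* power is about 73-76% when everyone starts at 2 mg/kg/day. Otherwise, unadjusted versus adjusted:

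| Escalated | Sites split | Loss (points) | All sites keep raised dose | Loss (points) |
|---|---|---|---|---|
| 10% to 3 mg/kg/day | 74% vs 75% | 1 | 73% vs 76% | 2 |
| 30% to 3 | 71% vs 75% | 3 | 71% vs 76% | 5 |
| 30% to 5 | 59% vs 73% | 14 | 51% vs 75% | 24 |
| 50% to 5 | 55% vs 75% | 20 | 47% vs 74% | 27 |

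Losses are taken before rounding.

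**4. What the recommended covariate can recover**

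The adjusted figures divide out the dose actually started. Where all sites keep the raised dose, that equals the last dose before randomization, so a pre-randomization covariate recovers nearly all of the loss. Where sites are split, the pre-randomization dose predicts the starting dose only in part, and only part of the loss comes back. The adjusted figures for split sites are therefore a ceiling. The single dosing rule and the covariate work together.

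**The case against.** Several stronger readings are tempting, and the documents do not support them.

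- **That two fixed doses flatly contradict each other.** Section 6.2.4.2 does not say the dose at entry. It says a stable dose and points to 5.7.2.4.1, so 2 mg/kg/day held stable until taper is a fair joint reading. The explicit reference to a stable dose from baseline concerns prophylaxis agents. Section 5.7.2.4.1 also allows discretion and local practice, so it is not a rigid dose for everyone. This stands: the defect is an unanswered question that admits two readings. Discretion does not answer it, because it leaves each site free to choose either.
- **That the same conflict arises for subjects entering below 2 mg/kg/day.** This is weak. Every route in criterion 3 requires primary treatment at 2 mg/kg or equivalent, and section 4.1 allows initiation.
- **That the endpoint is biased or no longer measures treatment.** Dose before entry is set before randomization and is balanced in expectation. The simulation agrees. Leaving it out costs precision only.
- **That open-label sites will treat escalated subjects differently by arm.** If they did, error would be inflated. With no true effect and 30% of subjects at an assumed 4 mg/kg/day, rejection is about 6.5% if 40% of escalated BEGEDINA subjects versus 60% of escalated controls keep the raised dose, and about 22% at 25% versus 75%. Nothing in the documents says this will happen. It is a reason to write one rule, not a finding about the trial.

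Section 8.0 defers further statistical detail to the SAP, and the document reviewed contains no SAP text beyond section 8. What can be said is that section 8.3.5.2 names GvHD grade as the only stratum. The endpoint also lies outside both testing sequences in section 8.3.5.1, which limits the stakes.

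**Conclusion.** The point holds in two limited parts.

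First, sections 4.1, 4.4.1, 5.7.2.4.1 and 6.2.4.2 do not make clear which background dose applies from Study Day 1 to a subject escalated before randomization. They must be reconciled.

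Second, the cumulative steroid analysis as described leaves out a pre-randomization variable that directly drives the outcome. The cost is precision on a tested secondary endpoint: about 1 to 20 points of power where sites split between the readings, and up to 27 in the most extreme setting with the raised dose kept everywhere. At the mild end the loss is close to simulation error. The escalated fraction, the raised dose, the SD and the effect are all assumed, so the figures show a plausible range and not a prediction. The randomized comparison stays valid provided that handling of the entry dose is unrelated to arm.

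**What to change.** 1. Reconcile sections 4.1, 4.4.1 (note to criterion 3), 5.7.2.4.1 and 6.2.4.2 into one rule for the background steroid dose from Study Day 1 in subjects escalated before randomization, the same in both arms. Which rule is the sponsor's clinical decision.
2. In section 8.3.5.2 and the SAP, adjust the cumulative steroid analysis for the last steroid dose before randomization, in methylprednisolone-equivalent mg/kg/day. Rank analysis of covariance within GvHD grade would serve, or entry-dose category as a further stratum. With few escalated subjects the covariance form is safer: at an assumed 10%, the extra category holds about 18 of 184 subjects, split over two grades.
3. Do not use the Study Day 1 dose as the covariate. Treatment starts on the day of open-label randomization (section 5.4), and section 5.7.2.3 recommends steroid premedication in the BEGEDINA arm only, so that dose can depend on arm.
4. Tabulate the pre-randomization dose by arm.

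The cost is one reconciled rule in the protocol, one covariate in the analysis and one table. No new data are needed: Table 19 and sections 5.7 and 6.2.4.2 already provide for recording prior medication with dose and dates, and weight is measured at screening.
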